#### Treatment and Clinical Follow-Up:

Patients enrolled in the “Accelerated Atherosclerosis in High Risk Population Groups: An Assessment by Magnetic Resonance Imaging” study will be evaluated in the cardiology clinic by [name],

FACC, FSCAI who is the Director of Peripheral Vascular Intervention at Emory University and treats patients with carotid artery disease. All these patients will be randomized based on the last digit of their medical record number. If the last digit will be an even number they will then be given a statin, which they will take and will also be instructed about regular exercise. Patients will be made aware of the side effects of statins and about the procedures to report these side effects. Patients with the last digit being an odd number will ONLY be advised about exercise. All patients will have regular visits and patients on a statin will be followed up and evaluated for any adverse effects of the medication and for compliance at 18 and 36 months by the study preventive cardiologist. The preventive cardiologist or any other physician involved with care of the patient may elect for more frequent follow up as well as modification or discontinuation of the study prescribed therapy if deemed necessary based on his or her best clinical judgment.

These patients will get routine clinical follow-up in the oncology (The Winship Cancer Institute Clinics) and cardiology clinics (Emory Hospital) as part of the ongoing routine clinical care.

Within five weeks of initial MRI evaluation, our recruited research that demonstrate increased blood markers and/or atherosclerosis on MRI would be subjected to life style modification ± medical (statin) therapy. Department of Cardiology would prescribe and monitor statin therapy: Rosuva (20 mg once a day) with target LDL goal < 70; non-HDL goal < 100 and Aspirin (81 mg once a day). The rational for using rosuva 20 mg is because this dosage has already been successfully used in JUPITER Trial (35). The follow-up by Cardiology department would comprise educating the patients on life style modification and also how to monitor and report any adverse drug affects which if expected would be further assessed with laboratory testing with LFT's and CBC. Any patients who suffer clinical side effects of treatment as part of our research would be taken off our study. Patients will continue to follow-up in the survivorship clinic and with the preventative cardiologist as indicated.

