The randomized therapy may be modified or discontinued at the discretion of any physician involved with a study patients' care or the study-designated preventative cardiologist based on clinical judgment. This may occur during scheduled follow up with the study-designated preventative cardiologist or at any point.

Life style modification will be tailored, implemented and followed up by Emory HeartWiseSM Risk Reduction Program. This Program will use several analytical tools including questionnaire (BOMC, Rose, FRAT, CHD Knowledge Test). These analytical tools, laboratory as well as imaging tests will help EmoryHeartWise Risk reduction Program devise the best life style modification and exercise strategy for our patients.

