### Baseline, Intermediate and Final MRI:

Each subject will undergo similar scan protocol at baseline, intermediate and final MRI. Anatomical landmarks will be used to match images (baseline, intermediate and final) in the same patient from the three time points spread over an intervals of 18 months. These landmarks include arterial bifurcations, vertebrae, proximity of other vessels and patterns of fat and muscle. Since the slice volume would be planned centered at the area of interest for all the studies (initial and repeat); the exact Z-location of each slice would be known and reproducible for acquisition and comparative measurements.

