Data analysis: The techniques described in sections above (A1 to A3) would be used in combination to determine plaque-remodeling, inflammation within the plaque and serum markers of inflammation and compare efficacy of different treatment regimens. Each patient will get MRI examinations before and after treatment and therefore patients will serve as their own control.

Expected results: We anticipate that the efficacy of comprehensive treatment would outperform the results obtained with life style modification alone.

We will carry out the modeling using SAS/STAT procedure MIXED.

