**Adverse Event Reporting:**

We do not expect any serious physical adverse events from this research study. Participating in this study involves very few/minimal risks. Study staff will work with patients to minimize any stress or discomfort with the study procedures. The study involves a blood draw, which may cause slight bruising or pain at the site where the blood is drawn. In addition, bleeding, dizziness, fainting or feeling lightheaded, nausea, hematoma or infection may occur because of drawing your blood. The blood will be drawn from expert/trained staff so this will be less likely to happen.

The Computed Tomography (CT) for coronary artery calcification (CAC) and Echocardiogram are both non-invasive procedures. CT exams are generally painless, fast and easy. The risks associated with CAC screening are small (48). The echocardiogram is very safe, painless and uses ultrasound waves, for which there are no known risks.

We do not expect any serious physical adverse events from MRI examinations. Due to recent concerns related to the use of gadolinium-based contrast agents in patients with renal dysfunction and risk of nephrogenic systemic fibrosis (NSF), serum creatinine levels will be measured from blood drawn before each MRI examination (49). Patients with normal renal function values will be administered contrast and this approach virtually eliminates any possibility of NSF.

Statin treatment might cause some side effects in few individuals which would be closely monitored by symptoms and followed by blood tests; if any side effects occur, the medication would be immediately stopped; patients would be taken off the study protocol and they would continue their routine follow up in The Survivorship and Cardiology clinics.

Subjects will be provided with telephone numbers of the PI, co-investigators and the Emory University IRB. Any adverse events will be appropriately documented and reported through the Department of Radiology Safety Committee.

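### Patients with side effects are taken off the study, not only off treatment, so follow-up outcomes are lost mainly from the statin arm and the aim 4 comparison can be biased

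*Combined protocol and SAP*

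**What the plan says.** The removal rule appears twice. Treatment and Clinical Follow-Up says: "Any patients who suffer clinical side effects of treatment as part of our research would be taken off our study". Adverse Event Reporting, on the statin, says: "if any side effects occur, the medication would be immediately stopped; patients would be taken off the study protocol". It then adds that "they would continue their routine follow up in The Survivorship and Cardiology clinics". Stopping the medication and leaving the protocol are listed there as two separate steps.

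The same sections show where the rule will bite. Adverse Event Reporting introduces it with "Statin treatment might cause some side effects in few individuals", and Treatment and Clinical Follow-Up says that "patients on a statin will be followed up and evaluated for any adverse effects of the medication". No matching adverse-effect evaluation is described for the exercise-only arm.

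A further paragraph of Treatment and Clinical Follow-Up says: "The randomized therapy may be modified or discontinued at the discretion of any physician involved". It does not say whether such a patient stays in the study for outcome measurement.

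The analysis and imaging sections are written as if all patients are followed. Specific Aims, A # 4, says: "Each patient will get MRI examinations before and after treatment and therefore patients will serve as their own control". Baseline, Intermediate and Final MRI says: "Each subject will undergo similar scan protocol at baseline, intermediate and final MRI". For aim 4 the plan names SAS PROC MIXED, but no analysis population, missing-data rule or sensitivity analysis.

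**The concern.** Aim 4 is the only between-arm efficacy question in the protocol. Its validity rests on comparing the two groups as they were allocated. If a side effect ends study participation, whether an outcome is measured depends on the arm (only one receives the statin) and on something that happens after allocation. The statin patients still observed at 18 and 36 months are then a selected subset, while the exercise-only arm stays largely intact. If removed patients would have had different plaque or marker outcomes, the arm difference is biased. Analysis cannot reliably restore outcomes that were never measured, so the remedy has to be in place while follow-up is under way.

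**Working it through.** **1. The passages side by side.** Both removal statements go beyond stopping the drug. After removal, the only follow-up provided is routine clinic care, plus cardiology follow-up as indicated. No section keeps the study MRI or bloods. The trigger in Adverse Event Reporting has no severity threshold. The loss falls mainly, though perhaps not only, on the statin arm: one section ties the rule to the statin, but the other speaks of treatment, which could include the exercise programme. A patient removed after the 18-month scan loses only the 36-month outcome.

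**2. The plan's own figure.** Sample Size gives 92 subjects, effect size 0.28, alpha 0.05 and power above 99%, from an ANOVA on three time points. With 3 groups of 92, noncentrality is 3 × 92 × 0.28² = 21.6 and power is 0.990, so the figure reproduces. It concerns aim 3. Aim 4 has no power calculation, and the attrition allowance of about 10% is not split by arm or cause.

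**3. Complete-case illustration.** Assumptions, none from the documents except the total of 100: about 50 patients per arm; a share p of statin patients removed before any follow-up scan; removed patients differ from retained ones by δ SD; no true arm difference.

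- Shift in arm difference = p × δ.
- SE with 45 evaluable per arm = √(2/45) = 0.211 SD (40 v 50: √(1/40 + 1/50) = 0.212).
- Two-sided type I error = Φ(−1.96 + shift/SE) + Φ(−1.96 − shift/SE).

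| Removed (p) | δ (SD) | Shift (SD) | Shift/SE | Type I error |
|---|---|---|---|---|
| 5% | 0.5 | 0.025 | 0.12 | 5.2% |
| 10% | 0.75 | 0.075 | 0.36 | 6.5% |
| 20% | 1.0 | 0.20 | 0.95 | 15.8% |

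**4. What a mixed model recovers.** Take the high case (20%, 1.0 SD) and an assumed visit correlation of 0.7. A likelihood analysis predicts the missing 36-month value from earlier visits.

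- Equal correlation between all visits: the slopes on baseline and on 18 months are each 0.7/1.7 = 0.412.
- First-order autoregressive (the structure named in Sample Size): the slope is 0.7 on 18 months and 0 on baseline.

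If removed patients differ at 18 and 36 months but not at baseline, removal before the 18-month scan leaves the full 0.20 × 1.0 = 0.20 SD. Removal after it leaves 0.20 × (1 − 0.412) = 0.12 under equal correlation, or 0.20 × (1 − 0.7) = 0.06 under autoregressive. If they differ equally at baseline too (equal correlation), the remainders are 0.20 × (1 − 0.7) = 0.06 and 0.20 × (1 − 0.824) = 0.035. The half-and-half column is from simulation.

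| Pattern | All removed before 18 months | Half | All removed after 18 months |
|---|---|---|---|
| Equal correlation, no baseline difference | 0.20 | 0.16 | 0.12 |
| Autoregressive, no baseline difference | 0.20 | 0.12 | 0.06 |
| Equal correlation, same difference at baseline | 0.06 | 0.04 to 0.05 | 0.03 to 0.04 |

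**5. Precision.** For a 0.5 SD effect, two-sample t-test power is 0.70 with 50 v 50 and 0.65 with 40 v 50. The issue is bias far more than lost numbers.

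**The case against.** The strongest reply is that the planned analysis is a mixed model, not a complete-case comparison. It uses all data collected before removal and is unbiased if outcomes are missing at random given those data. The type I error figures above are not for that model. If side-effect patients already differ at baseline, most of the shift disappears, as the last row of the second table shows. Adverse-effect evaluation is scheduled at 18 and 36 months, so some removals would follow the 18-month scan. The protocol expects few side effects, and at low removal rates the effect is small.

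All of this stands as a limit on size. It does not remove the problem. A patient removed before 18 months contributes only baseline, and nothing in the plan supports or tests the missing-at-random assumption.

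It can also be said that the statements about each patient's scans are ordinary schedule descriptions, not claims of complete data. That is fair: they are not a separate defect, but they show that the plan does not say what happens to removed patients. The attrition allowance is no answer either way, because it is an overall figure for other aims.

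Finally, removal may be meant to protect patients, and study visits involve gadolinium contrast. That is a reason to word the change with care. It is not a reason to leave outcome collection undefined.

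**Conclusion.** The concern holds. As written, a side effect ends study participation, no passage keeps the remaining outcomes, and the loss falls mainly on the statin arm. The direction and size of the bias cannot be known from the documents. Under the stated assumptions the complete-case shift runs from 0.025 to 0.20 SD. In the high case a likelihood model leaves between about 0.03 and 0.20 SD, depending on when patients are removed, the visit correlation and whether they already differ at baseline. The finding rests on the wording of the removal rule, not on these figures. It should be fixed, because the change is cheap and outcomes not measured cannot be collected later.

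**What to change.** Reconcile the removal sentence and the physician-discretion paragraph in Treatment and Clinical Follow-Up with Adverse Event Reporting. Decisions on stopping or changing medication stay with the physicians, and no clinical rule is proposed here. Then state:

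- Stopping treatment does not by itself end study follow-up. Every allocated patient who still consents keeps the remaining planned 18- and 36-month MRI and blood tests, subject to the existing pre-scan safety checks, including creatinine.
- The main aim 4 analysis includes all patients in their allocated arm regardless of adherence. An on-treatment analysis is a sensitivity analysis only.
- The number, timing and reasons of removals are reported by arm.

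The cost is a protocol amendment and consent wording. The visits are already planned for every subject, but Other tests says that funding for some tests was still to be sought, so the retained visits are not shown to be budgeted. The statistical downside is that the estimated effect of assignment may be diluted by patients who stop the statin.

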### **Emory HeartWiseSM Risk Reduction**

*Joint Proposal WCI/Preventive Cardiology- Emory HeartWiseSM Risk Reduction:*

Lifestyle Modifications in our high-risk patients with Subclinical Atherosclerosis  
12 week/3 months; 3 x / week, total 36 visits

Recommend 6 Minute Walk Test (MWT) on Telemetry for each Patient: functional screen

Evaluation:

1. A 6 Minute walk test on telemetry – screening tool for function and cardiovascular/hemodynamic response.
2. PHQ-9 (Patient Health Questionnaire) depression questionnaire
3. Risk stratification – ACSM (American College of Sports Medicine) guidelines

[figure not shown]
Exercise components:

1. Create exercise prescription based on ACSM guidelines and results of 6 MWT.
2. Orientation: safety principles of exercise, waist hip circumference; BMI (Body Mass Index); risk factor identification.
3. Brief meeting with Registered Dietitian (RD) for review of food intake/diary.
4. 1x/month 10 -15 minute meeting with RD for review of food intake and plan.
5. Minimum of 3x/week exercise program – based on FITT (frequency, intensity, time, and type) principles.
6. Individualized exercise prescription created and progressed by staff; tracked on flow sheets; monitor blood pressure; if diabetes - Blood Glucose (BG) pre/post/during if necessary.

The Healthy Exercise for Lymphoma Patients (HELP) trial was a randomized controlled trial looking at the benefits of 12 weeks supervised exercise program for cancer survivors compared to usual care (36). Improvements in health-related fitness and quality of life were maintained at the 6-month clinical follow up. The same model of secondary prevention through supervised, graded exercise as well as identifying and intervening with education and active participation in risk factor modification is being proposed to help high-risk patients identified with subclinical atherosclerosis.

The premise of inclusion of exercise regimen in our study is that regular, moderate levels of exercise have been shown to be beneficial at lowering blood pressure, total cholesterol, low-density lipoprotein, triglycerides, increasing high density lipoprotein, metabolic syndrome, insulin sensitivity, and all-cause mortality (37). Intensive lifestyle modification through education, support, and supervised exercise are the core components directed at risk factor reduction (38). Fig 3. (below) demonstrates risk factor modification for patients who completed a 12 weeks cardiac rehabilitation program compared to a larger cohort of cardiac rehabilitation patients in other parts of the country (39). The same model of prevention through supervised, graded exercise as well as identifying and intervening with education and active participation in risk factor modification is being proposed to help high-risk patients with subclinical atherosclerosis.

Fig 3: Shows Cardiac Rehabilitation Program Outcomes 2008

### **MRI Examination:**

Pre-MRI screening and informed consent:

Upon arrival at the MRI Research Center, a trained MRI technologist will screen each study participant for metal objects and implants that may be hazardous in the MRI environment. The subject will be given a copy of the informed consent form. The PI or the co-investigator will be responsible for ensuring that the subject fully understands the procedure, for answering any questions the subject may have and for obtaining written informed consent. The technologist will then guide the subject to the MRI scanner room.

Imaging protocol:

All scans will be performed on a 3.0T MRI scanning system using 4-channel dedicated coil. A fast gradient echo 3-plane localizer will be performed to locate the major artery and its bifurcations. The location and extent of the lesion will be ascertained or verified from the 3D-TOF angiographic images (described below). The site of imaging will be selected to coincide with the location of a selected known lesion. The acquired axial images and the MIP formatted images will both be used to verify the region of stenosis and will be used to prescribe the high-resolution anatomical images (described below). Five to ten imaging locations will be prescribed depending on the known extent of the lesion. Double-oblique sections will be acquired for optimal visualization of the artery plaques for all the sequences described below.

### Three-Dimensional time-of-flight MR angiography:

An axial three-dimensional spoiled gradient echo (3D-SPGR) MR angiogram will be used for scout images and to locate regions of stenosis. The acquisition will consist 40 to 60 contiguous slices. A field-of-view (FOV) of 12 cm to 16 cm at the region of interest will be used. Additional scan parameters are: Slice thickness = 2.0 mm, matrix = 256 x 256, receiver bandwidth = 32 KHz, flip angle = 45°, TR = 32 ms, TE = 4.7 msec, number of signal averages = 2. Maximum-intensity pixel projection (MIP) images will be created from all the image sections obtained during the 3D-SPGR acquisition.

### High Resolution Anatomical Images:

T1 weighted (T1W), T2 weighted (T2-W) and proton density weighted imaging (PDWI) using a double inversion-recovery fast spin echo sequence and 3-point Dixon (3-PD) imaging will be performed. All black-blood scans will be cardiac gated. The following scanning parameters will be common to all three of the contrast-weighted scans: Section thickness = 2.0 mm, matrix = 512 x 384, receiver bandwidth = 62.5 KHz, ETL = 24, FOV: right-left - 12 cm to 16 cm; anterior-posterior – 0.75 \* right-left dimension, Number of signal averages = 2. The specific weighting parameters are: T1-W: TE = 10 ms, TR = 1 R-R interval; T2-W: TE = 45 ms, TR = 2 R-R intervals; PDW: TE = 10 ms, TR = 2 R-R intervals.

### DCE 2D SPGRI:

Dynamic contrast-enhanced (DCE) two-dimensional T1-W SPGR pulse sequence will be used for dynamic contrast-enhanced imaging of the arterial plaque. The following scan parameters will be used: Slice thickness = 2.0 mm, FOV: right-left - 12 cm to 16 cm; anterior-posterior – 0.75 \* right-left dimension, matrix = 256 x 160, receiver bandwidth = 32 KHz, flip angle = 60°, TR = 120 ms, TE = 2.9 msec. Twelve to fifteen double-oblique slices will be acquired during each scan. The orientation of the slices will be the same as those of the black-blood images. A baseline non-contrast scan will first be acquired. Then 0.1 mmol/kg of Gd-DTPA will be injected by a power injector at a rate of 2 mL/sec simultaneous to the contrast enhanced acquisition. A total of 20 similar image acquisitions will be performed with no time elapsing between scans after the injection.

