#### Assessment of Arterial Plaques by Measuring Contrast Agent Dynamics Using MR Images:

The dynamics of the contrast enhancement will be quantified using a generalized kinetic model that was proposed by Tofts, et al (45) which is based on two compartments, the blood plasma and the extravascular extracellular space (EES).  $K_{trans}$  and

model, which assumes that the signal intensity of the contrast agent in the tissue compartment and the blood plasma compartment are linearly proportional to the total concentrations of the contrast agent in the tissue,  $C_t$  and the blood plasma,  $C_p$  (42, 43, 45). This approach assumes that there is an exponential decay in the concentration of the contrast agent in the plasma described by the equation, where  $A_i$  is the initial plasma concentration and  $m_1$  is the plasma signal decay rate.

For e.g. in case of carotid arteries, the values for  $A_i$  and  $m_1$  will be determined by an ROI placed in the lumen of the jugular vein on each image in the time-course at each section location.  $C_t$  will be found by identifying regions of enhancement within the plaque. A sample of pixels large enough to cover the enhancing regions will be taken. The average of the sample pixels for each image at a given location will be used as input values for the kinetic model. The kinetic analysis will be performed using a workstation tool by the two co-investigators and repeated to assess for the inter-observer and intra-observer variability.

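### One pre-contrast DCE frame is the reference for 20 post-injection frames; a few more baseline frames are a cheap precision gain, clearest for the second kinetic parameter and uncertain for Ktrans

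*Combined protocol and SAP*

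**What the plan says.** The DCE 2D SPGRI section sets out the dynamic series. Before contrast: "A baseline non-contrast scan will first be acquired". The injection is then given "simultaneous to the contrast enhanced acquisition", and "A total of 20 similar image acquisitions will be performed with no time elapsing between scans after the injection". No other pre-contrast DCE acquisition is planned. The settings that determine frame duration are "flip angle = 60°, TR = 120 ms" and "matrix = 256 x 160", with the front-to-back field of view at 0.75 of the left-right dimension. The section does not state the number of signal averages; the angiographic and anatomical sequences each state two.

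The section on measuring contrast agent dynamics uses a two-compartment kinetic model. It takes the contrast-agent signal as "linearly proportional to the total concentrations of the contrast agent in the tissue", and likewise for plasma. On the model inputs it says: "The average of the sample pixels for each image at a given location will be used as input values for the kinetic model". It does not say whether the baseline is subtracted, used as a divisor or fitted, nor how many parameters are free. The plasma decay rate is to come from a jugular vein ROI. The only variability check is repeated analysis by two co-investigators; no repeat scan is planned.

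**The concern.** Tissue gives signal before any contrast arrives, so a concentration curve needs a pre-contrast reference. If that reference is one frame, its noise moves the whole curve up or down together. The 20 later frames do not dilute this, because each is compared with the same reference. A kinetic fit can read a constant offset as immediate plasma enhancement and, in some fits, as a change in Ktrans.

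Ktrans and the second DCE parameter are the plaque inflammation measures for Aims 2 and 3, and Aim 4 reuses them. Random error in them weakens the Aim 2 correlations with serum markers. It flattens the Aim 3 slope where they predict vessel wall area, and it widens the Aim 4 comparison. Re-reading the same images would not reveal the error, since every reading uses the same baseline frame.

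**Working it through.** The plan states no precision figure for the DCE parameters, so there is none to reproduce.

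**Inputs from the protocol.** Baseline frames n0 = 1; post-injection frames 20; TR 120 ms; 160 phase-encoding lines; signal linear in concentration.

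**Assumptions.** Enhancement is a difference from the baseline signal. Noise is equal and independent between frames, with variance s². There are 160 lines per frame, or 120 if the 0.75 field of view reduces them. Plasma decay is mono-exponential at 0.05-0.3 per min, and washout is 0.08-0.8 per min. Frames are timed at their midpoints, and the plasma curve is noise-free. The second parameter is a plasma fraction.

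**Step 1: frame duration.** 160 × 0.120 s = 19.2 s; 120 × 0.120 s = 14.4 s.

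**Step 2: noise in enhancement.** The covariance of the 20 differences is s²(I + J/n0), where J is the all-ones matrix. At n0 = 1:
- Each value has variance 2s², and any two share covariance s², so their noise correlation is 1/2 = 0.50.
- Mean enhancement has variance s²(1/20 + 1) = 1.05s². The baseline frame's share is 1/1.05 = 95%.
- Doubling to 40 post-injection frames would give 1/40 + 1 = 1.025s², almost no gain.
- At n0 = 5 the variance is s²(1/20 + 1/5) = 0.25s². The baseline contribution has fallen by 1 − 1/5 = 80%.

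**Step 3: into the parameters.** In least squares with A = (X'X)⁻¹X', where X holds the model's derivatives with respect to its parameters, Var = s²[diag(AA') + (A1)²/n0]. If p is the share of a parameter's noise variance due to the baseline frame at n0 = 1, then SD(5 frames)/SD(1 frame) = √(1 − 0.8p).

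Worked example: 19.2 s frames, plasma decay 0.2 per min.
- Two parameters, no backflux. An offset b, in units of initial plasma concentration, is fitted exactly, because 1 = e^(−mt) + m × (1 − e^(−mt))/m. It adds b to the plasma term and m × b to Ktrans. The shares are p = 0.78 (plasma) and 0.70 (Ktrans). The SD ratios are √(1 − 0.624) = 0.61 and √(1 − 0.56) = 0.66.
- Three parameters, washout about 0.5 per min. The shares are p = 0.56 (plasma) and 0.00 (Ktrans). The SD ratios are √(1 − 0.448) = 0.74 and 1.00.

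Fall in SD over the assumed ranges:

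| Fit | Parameter | 1 to 5 baseline frames | 2 to 6 (first dynamic frame contrast-free, 19 left) |
|---|---|---|---|
| Two parameters, no backflux | plasma term | 37-42% | 23-27% |
| Two parameters, washout fixed above zero | plasma term | as little as about 9% | as little as about 5% |
| Three parameters | plasma term | 21-32% | 11-18% |
| Two-parameter fits | Ktrans | about 3-44% | also smaller |
| Three parameters | Ktrans | 0-8% | at most 3% |

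Sensitivity: with plasma decay 0.1-0.4 and washout 0.3-1.0 per min, the plasma-term gains are 35-41% (no backflux) and 20-28% (three parameters). The three-parameter Ktrans gain is then 0-12%.

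**Step 4: into correlations.** Let f be the noise share of total observed variance and c the cut in SD. The observed correlation is multiplied by 1/√(1 − f + f(1 − c)²).
- f = 0.30 (reliability 0.70): c = 0 gives no change; c = 0.08 gives 1/√0.954, or +2%; c = 0.21 gives 1/√0.887, or +6%; c = 0.42 gives 1/√0.801, or +12%.
- f = 0.05: c = 0.42 gives 1/√0.967, or +1.7%.

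**The case against.** The strongest reply is that this refines a workable plan and corrects no error. Nothing in the documents is contradicted, no analysis is invalidated and neither arm is favoured. All of that stands.

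The size is also open. Averaging over the enhancing pixels already reduces random noise in every frame, and no signal-to-noise ratio, ROI size or scan-rescan figure is given. At a 5% noise share the gain in correlation is under 2%. Baseline subtraction is inferred; a freely fitted baseline would change the error structure. With injection at the start of the series and frames of 14-19 s, the first dynamic frame may act as a second baseline. Extra frames do not correct misregistration between baseline and series, although with several frames a visibly corrupted one can be dropped. These points limit the size of the benefit but do not remove the shared error.

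A reader might infer that the baseline noise passes undiminished into both kinetic parameters. The documents do not support that: they leave the number of free parameters open, and in a three-parameter fit Ktrans is almost unaffected. A reader might also infer a dependable rise in correlations of 5% or more. That needs noise near 30% of total observed variance and one of the more favourable fits. If noise were instead 30% of true between-patient variance, reliability would already be 1/1.3 = 0.77.

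**Conclusion.** The point holds as a low-cost improvement. If enhancement is measured against the single planned baseline frame, that frame's error is common to the whole curve, and five frames would remove 80% of its variance. The benefit for the second parameter is present in every fit examined, from about 9% to 42% in SD, or about 5% to 27% if the first dynamic frame is contrast-free. For Ktrans it runs from nothing to about 44%, depending on the fit. These floors would be lower if frames were timed at their ends.

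The effect on observed correlations is 0-12% if noise is 30% of total variance and under 2% if it is 5%; both shares are assumptions. The conclusion rests on baseline subtraction, equal independent frame noise, and reading the lost symbol as a plasma fraction. It does not show that the DCE measures are unreliable as planned, or that the treatment comparison is biased.

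**What to change.** In the DCE 2D SPGRI section, replace the single non-contrast scan with about five identical pre-contrast acquisitions before the injection, and keep the 20 post-injection acquisitions. State the number of signal averages there.

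In the section on contrast agent dynamics, define the pre-contrast signal, for plaque and jugular ROIs alike, as the mean of those frames after dropping any with visible motion. State how it enters the model and which parameters are fitted.

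Use the same number of baseline frames at all three visits of a patient. The protocol is at Version 3 and scanning may have begun, so apply the change only to patients whose first scan has not yet taken place.

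Cost: four extra frames per visit. With one signal average this is 4 × 14.4 = 57.6 s to 4 × 19.2 = 76.8 s; with two it is 115.2 to 153.6 s. No added contrast, visit or reader is needed.
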